9.3.2 Outcomes

9.3.2.1 Primary Outcome

- Outcome name: stroke and systemic embolism
- Time frame: drug exposure period
- Safety issue. N/A
- Definition: definition of stroke and systemic embolism provided in Koretsune et al will be used for this study⁸ as following.
 - ✓ Stroke: all three following conditions must be met:
 - [1] Imaging (magnetic resonance imaging (MRI) or computed tomography (CT)) is performed after a diagnosis code of atrial fibrillation.
 - [2] Diagnosis of stroke defined as I60-I64 occurs in the same month as the imaging
 - [3] Either of the following condition is met:
 - A) Rehabilitation for cerebrovascular disease within 30 days from the date of imaging
 - B) Death within 30 days from the date of imaging
 - ✓ Systemic embolism events:
 1. Retinal vascular occlusions: three following conditions must be met:
 - [1] Ophthalmic examination is performed after the date of definitive diagnosis of atrial fibrillation or cardioembolic stroke (including the day of the diagnosis).
The second or later ophthalmic examination during the same hospitalization is excluded.
 - [2] Diagnosis of retinal vascular occlusion in the month of the date of ophthalmic examination.
 - [3] The following A) and B) are satisfied:
 - A) Prescription of anticoagulant/antiplatelet agents on the day of ophthalmic examination or the next day
 - B) Non-prescription of anticoagulant/antiplatelet agents within 30 days from the date of ophthalmic examination.
 2. Other than retinal vascular occlusions: four following conditions must be met:
 - [1] Imaging: MRI, CT, roentgenography (using a contrast medium) or vascular echo is performed after the date of definitive diagnosis of atrial fibrillation or cardioembolic stroke (including the day of the diagnosis).
 - [2] Systemic embolism (including the name of injury/disease at the time of admission) is diagnosed and recorded as the name of the disease during hospitalization in the month of the date of imaging.
 - [3] The date of imaging or the next day: Treatment
Either of the following conditions is satisfied:
 - A) Treatment with heparin at >5,000 units or thrombectomy on the day of imaging or the next day
 - B) Death within 30 days from the date of imaging

✓ [4] Fees for emergency medicine administration or specific intensive care management on the day of imaging are calculated.

Intracranial bleeding: all four following conditions must be met:

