Condition [1] is applied to the events occurred during the hospitalization after the day of definitive diagnosis of atrial fibrillation and is not applied to those during re-hospitalization.

[1] Medical history (only atrial fibrillation)

The following injury/disease name in ICD 10 does not occur in the month prior to the month of the date of definitive diagnosis:

- Cerebrovascular disease excluding sequelae of subarachnoid hemorrhage, sequelae of intracerebral hemorrhage, sequelae of stroke not specified as hemorrhage or infarction
- Intracranial injury

[2] Imaging (MRI or CT) is performed after the month of the date of definitive diagnosis of atrial fibrillation or cardioembolic stroke (including the day of the diagnosis).

The second or later imaging during the same hospitalization is excluded.

[3] Disease name

The following disease occurs in the same month as the day of imaging:

- Cerebrovascular diseases excluding sequelae of subarachnoid hemorrhage, sequelae of intracerebral hemorrhage, sequelae of stroke not specified as hemorrhage or infarction
- Intracranial injury

[4] Rehabilitation of stroke

Either of the following conditions is satisfied:

- Rehabilitation for stroke within 30 days from the date of imaging
- Death within 30 days from the date of imaging

See below tables for definition of imaging (Table 2) and other symptoms/diseases/treatment (Table 3).

Table 2 Definition of imaging for primary outcome

| Receipt code | Definition |
|----------------------|---|
| 170011810 | CT imaging (multi-detector computed tomography) |
| 170020110 | MRI imaging (equipment with 1.5+ tesla) |
| 170033410 | CT imaging (multi-detector computed tomography) |
| 170033510 | MRI imaging (equipment with 3+ tesla) |
| 170000810 | Roentgenography (with contrast agent) |
| 160147110, 160147210 | Vascular echo |
| 160150050, 160161710 | |

Table 3

Definition of symptoms/diseases/treatment for primary outcome

| Symptoms/diseases/treatment | Definition | | |
|-----------------------------------|--------------|--|----------|
| | ICD10 code | Receipt code | ATC code |
| Atrial fibrillation | I48 | | |
| Stroke | I61-64 | | |
| Rehabilitation | | 180027410, 180027510 180027610, 180027710 180030810, 180032410 180032510, 180032610 180033910, 180034010 180034110, 180034210 180034310, 180034410 180043430, 180043530 180043630, 180043730 180043830, 180044310 | |
| Cerebrovascular disease | I60-I69 | | |

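### Condition [2] of the intracranial bleeding rule under the primary outcome gives two incompatible time anchors, so events imaged in the month of diagnosis may or may not count depending on how it is coded

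*Combined protocol and SAP*

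**What the plan says.** Section 9.3.2.1 (Primary Outcome) lists four claims-based rules. Their timing conditions are:

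- **Stroke, condition [1]:** imaging "is performed after a diagnosis code of atrial fibrillation".
- **Retinal vascular occlusion, condition [1]:** "Ophthalmic examination is performed after the date of definitive diagnosis of atrial fibrillation or cardioembolic stroke (including the day of the diagnosis").
- **Other systemic embolism, condition [1]:** imaging up to and including "vascular echo is performed after the date of definitive diagnosis of atrial fibrillation or cardioembolic stroke (including the day of the diagnosis").
- **Intracranial bleeding, condition [2]:** MRI or CT "performed after the month of the date of definitive diagnosis of atrial fibrillation or cardioembolic stroke (including the day of the diagnosis").

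The last rule is conjunctive: "Intracranial bleeding: all four following conditions must be met". It also limits which scan may be used: "The second or later imaging during the same hospitalization is excluded". The section sets the window for the outcome as "Time frame: drug exposure period". Section 9.2 starts drug exposure at the index date and follow-up on the day after it.

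**The concern.** Only the intracranial bleeding rule anchors on a month, and it then adds a parenthesis that makes sense only with a date. A programmer has to discard one half of the sentence, and nothing else in the document says which half.

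The choice matters for patients who start the drug in the calendar month of their diagnosis. If the month wording is coded, these patients accrue treated time at the start of follow-up in which this rule cannot produce an event. All four conditions are required, so failing [2] alone removes the event from the rule. A scan in the following month of the same stay cannot recover it, because only the first scan of a hospitalization is eligible.

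Section 7 also cites a positive predictive value of 85.0% for a claims definition of intracranial haemorrhage. That figure supports this study only if the rule as coded is the rule that was validated.

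**Working it through.** The plan states no figure that depends on this condition, so there is none to reproduce. The check is a comparison of texts, followed by an illustration of scale.

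**1. What each reading admits.** Take AF diagnosed on day 10 of a 30-day month.

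| Reading of condition [2] | Scan day 5 | Scan day 10 | Scan day 20 |
|---|---|---|---|
| Strictly after the month | no | no | no |
| After the month, diagnosis day as an exception | no | yes | no |
| On or after the date | no | yes | yes |
| From the diagnosis month onward | yes | yes | yes |

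The four readings give four different patterns. If drug starts on or after the diagnosis date, the one-day exception recovers almost nothing, because follow-up begins the day after the index date.

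**2. Which reading the surrounding text favours.** Both systemic embolism rules pair the same parenthesis with a date. The preamble to condition [1] of the bleeding rule speaks of events in the hospitalization following the day of AF diagnosis, so it expects early events to be assessed. Condition [1] screens for earlier disease in the month before the diagnosis month. If [2] opened only after the diagnosis month, that month would be neither history nor eligible time. This points to a date anchor but does not prove it.

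**3. What the composite could lose.** Condition [3] of the bleeding rule admits cerebrovascular disease (I60-I69 in Table 3) less three sequelae codes (I690, I691, I694), plus intracranial injury (S06). The stroke rule has no month restriction on imaging after the AF code, has the same rehabilitation-or-death criterion within 30 days, and requires: "Diagnosis of stroke defined as I60-I64 occurs in the same month as the imaging". Subtracting one set from the other:

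- (I60-I69 less I690, I691, I694, plus S06) less (I60-I64) = S06 and the I65-I69 codes other than I690, I691 and I694.
- Table 3 defines stroke as I61-64. If the table governs over the text, I60 joins the list.

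**4. Length of the blank window.** The documents do not give the interval between diagnosis and drug start, so this part rests on assumptions: a 30-day month, diagnosis equally likely on each day d, and the month wording coded strictly.

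- Drug started on the diagnosis day: window = 30 − d days, from 0 to 29. Mean = (0 + 1 + … + 29)/30 = 435/30 = 14.5 days.
- Drug started on a day equally likely from d to 30: the mean halves, 14.5/2 = 7.25 days.
- Drug started after the diagnosis month: 0 days.

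For scale, Table 9 uses a follow-up of 0.40487 years, and 0.40487 × 365.25 = 147.9 days. Against that, 29 days is 29/147.9 = 19.6%, 14.5 days is 9.8%, and 7.25 days is 4.9%. These percentages apply to an affected patient under this rule only. The table does not say that its follow-up figure is a mean.

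**The case against.** The other side has a good deal to say, and most of it limits the consequence without removing the contradiction.

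- **The parenthesis is as literal as the month.** It is wrong to say that the text plainly drops diagnosis-month events. The text is ambiguous, and the loss arises only under one coding. This stands.
- **No visible analysis is tied to the rule.** Section 9.7.1 plans hazard ratios for stroke/SE and major bleeding, and Kaplan-Meier output for ischemic stroke and major bleeding. Major bleeding has its own code list in 9.3.2.2, with no imaging condition. A reader might infer that a separate intracranial bleeding count would lose every diagnosis-month bleed, but no visible passage plans such a count and redacted sections cannot be assumed to. Nor does any passage state that intracranial bleeding is part of the composite. The rule is, however, set out under the primary outcome, so its role needs stating.
- **A percentage of lost follow-up is tempting.** Multiplying the window by a guessed share of same-month starters gives a figure, but the share has no source in the documents. Unscorable time under this rule is also not a loss to the composite, since I60-I64 events pass through the stroke rule.
- **The anchor is wider than AF.** An earlier cardioembolic stroke diagnosis could satisfy condition [2], so even the strict coding would not remove all such events.
- **Bias in the hazard ratio does not follow.** Time from AF diagnosis to anticoagulant start is a propensity score covariate (9.3.3), so the affected share should be similar in the matched arms. Nothing in the documents shows a differential effect.
- **The intended anchor lies in the cited validation study, which is not available here.** That is a reason to check the source before changing the wording. It does not justify leaving two anchors in the text.

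**Conclusion.** The contradiction is real, and nothing elsewhere in the document resolves it. If coded as strictly after the month, the rule cannot register an event imaged in the diagnosis month for patients who start drug in that month.

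The consequence for the stroke/SE composite is confined to events that only this rule admits (S06, the I65-I69 codes not excluded as sequelae, and I60 if Table 3 governs), and arises only if the rule feeds the composite. The window is 0 to about 29 days per affected patient, assuming a 30-day month and drug start on or after diagnosis. The number of events lost cannot be computed, because neither the share of same-month starters nor the rate of the residual codes is given.

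The documents do not support a claim of bias between arms, or of a general loss of early intracranial bleeds from the primary outcome. The point is worth acting on because it is an error in an outcome rule, two programmers could produce different counts, and it is cheap to correct.

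**What to change.** 1. In condition [2], replace the wording *after the month of the date* with *on or after the date*, and drop the parenthesis, which is then redundant. This matches both systemic embolism rules. Confirm it against the cited validation definition before coding.
2. Keep the requirement that the event falls within the drug exposure period, and apply it to the bleed itself as well as to the scan. Condition [1] cannot do this alone: it screens only the month before the diagnosis month. Condition [3] matches diagnosis to scan by month, so a bleed coded earlier in the diagnosis month, before drug start, could otherwise be paired with a later scan.
3. Add one sentence stating whether the intracranial bleeding rule feeds the stroke/SE composite.

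Cost: one phrase and one sentence in 9.3.2.1, a small change to the outcome code, and a check of the source definition. No change to the data extract or the planned models.

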9.3.2.2 Secondary Outcome

- Outcome name: Major bleeding
- Time frame: drug exposure period
- Safety issue. N/A
- Definition: major bleeding is defined as any bleeding associated with hospitalization and/or blood transfusion (defined as MDV procedure code K920) claims. Bleeding will include the following diagnostic names with ICD 10 codes in the parenthesis, and the list is inclusive, not exclusive;
 - ✓ Subarachnoid hemorrhage (I60)
 - ✓ Intracerebral hemorrhage (I61)
 - ✓ Digestive tract hemorrhage (K922, K290)
 - ✓ Hemorrhage, not elsewhere (R58)
 - ✓ Intraocular Hemorrhage (H113, H313, H356, H431)

- ✓ Hematuria (R31, N028, N029)
- ✓ Excessive Menstruation, Hemorrhage from Uterus (N93)
- ✓ Hemathrosis (M250)
- ✓ Hemopericardium (I312)
- ✓ Hemoptysis, bleeding from airway (R04)
- ✓ Hematemesis (K920)
- ✓ Epistaxis (R040)
- ✓ Acute post-hemorrhagic anemia (D62)

9.3.3 Covariates

Logistic regression model was used to estimate propensity scores based on all covariates listed below:

- ✓ Age
- ✓ Gender
- ✓ Speciality of prescribers of OAC
- ✓ Time from AF diagnosis to initiation of OAC
- ✓ History of stroke or transient ischemic attack yes/no
- ✓ History of myocardial infarction yes/no
- ✓ History of coronary artery disease yes/no
- ✓ History of heart failure yes/no
- ✓ History of diabetes mellitus yes/no
- ✓ History of dyslipidemia yes/no
- ✓ History of arterial hypertension yes/no
- ✓ History of peripheral artery disease yes/no

- ✓ History of peptic ulcer disease yes/no
- ✓ History of dementia yes/no
- ✓ History of malignant lymphoma yes/no
- ✓ History of leukemia yes/no
- ✓ History of solid tumor cancer yes/no
- ✓ History of kidney impairment yes/no
- ✓ History of liver disease yes/no
- ✓ History of valvular disease yes/no
- ✓ History of bleeding (gastro-intestinal, etc.) yes/no
- ✓ History of hospitalization yes/no
- ✓ CHA₂DS₂-VASC
- ✓ HAS-BLED Score
- ✓ Year of Initiating Treatment
 - Index date falling within 12 months starting from 14th of March in 2011 and then from 1st of March of each respective year in 2012 to 2016, then to 30 June 2016.
- ✓ Concomitant medication (prescription claims within the baseline period)
 - yes/no for the following:
 - ◊ aspirin
 - ◊ ticlodipine
 - ◊ cilostazole
 - ◊ clopidogrel
 - ◊ angiotensin receptor blockers or angiotensin converting enzyme inhibitors
 - ◊ beta-blocker
 - ◊ amiodarone
 - ◊ procainamide
 - ◊ disopyramide
 - ◊ flecainamide
 - ◊ pilcicainide
 - ◊ procainamide
 - ◊ calcium-channel blocker
 - ◊ digoxin
 - ◊ diuretics
 - ◊ statins
 - ◊ proton-pump inhibitor
 - ◊ H₂ receptor antagonist

The disease, condition/disease for AF risk score calculation, AF risk score, and concomitant medication are defined as [Table 4](#), [Table 5](#), [Table 6](#), [Table 7](#), [Table 8](#).

Table 4

Definition of clinical history

| Disease | Definition | |
|-------------------------------------|---|---|
| | ICD10code | prescription |
| Stroke or transient ischemic attack | I60-I64, G45 | - |
| Myocardial infarction | I21-I23 | - |
| Coronary artery disease | I251 | - |
| Heart failure | I110, I130, I132, I420, I50 | Prescribed furosemide (defined by generic name) |
| Diabetes mellitus | E100, E101, E109, E110, E111, E119, E14 | Prescribed drugs used in diabetes (defined by ATC code as A10) |
| Dyslipidemia | E78 | - |
| Arterial hypertension | I10-I15 | Prescribed 2 or more types of anti-hypertensive (defined in Table 2b) |
| Peripheral artery disease | I702-I709, I71, I739 | - |
| Peptic ulcer disease | K22, K25-K28 | - |
| Dementia | F00-F03, G30 | - |
| Malignant lymphoma | C81-C88 | - |
| Leukemia | C90-C96 | - |
| Solid tumor cancer | C00-C80, C97 | - |
| Kidney impairment | N28 | - |
| Liver disease | K70-K77 | - |
| Valvular disease | I059, I089, I358, I38, I48 | - |
| Bleeding (gastro-intestinal, etc.) | K25-K29, K922 | - |

Table 5 Definition of anti-hypertensive

| Class/type | ATC code |
|--|---|
| Calcium channel blockers (CCB) | C08A0 |
| Angiotensin receptor blockers (ARB) | C09C0 |
| Angiotensin converting enzyme inhibitors (ACE) | C09A0 |
| Diuretics | C03A1, C03A2, C03A3, C03A7, C03A9 |
| Thiazide diuretic | C03A3 (Thiazide, plane), C02D0 (Rauvolfia alkaloids) |
| Beta blocker | C07A0 |
| Alpha-adrenoreceptor antagonists | C02A2 |
| Potassium-sparing agents | C03A1 |
| Others | C02A1 (Antihypertensives), C02A3 (Antihypertensives for pulmonary arterial hypertension), C09X0 (Other agents acting on the renin-angiotensin system) |
| Combination agents | C09D1 (ARB and diuretics), C09D3 (ARB and CCB) |

Table 6

Definition of condition/disease for AF risk score calculation

| Condition/disease | Definition | |
|---|---|--|
| | ICD10code | prescription |
| Congestive heart failure or left ventricular dysfunction | I110, I130, I132, I420, I50 | Prescribed furosemide (defined by generic name) |
| Stroke (ischemic stroke, transient ischemic disease, or systemic embolism) | I63, I64, G45, I74 | |
| Vascular disease (myocardial infarction, peripheral arterial disease, or aortic plaque) | I21-I23, I702-I709, I71, I739, I700 | |
| Abnormal renal function | I12, I13, N00-N05, N07, N11, N14, N17-N19, Q61 | |
| Abnormal hepatic function | B150, B160, B162, B190, K704, K72, K766, I85 | |
| Stroke (ischemic stroke or transient ischemic attack) | I63, I64, G45 | |
| Bleeding | I60, I61, I62, D62, J942, H113, H356, H431, N02, N95, R04, R31, R58, K250, K260, K270, K280, K290, S063, S064, S065, S066 | Aspirin and clopidogrel: defined by general name |
| Drugs (aspirin, clopidogrel, or non-steroidal anti-inflammatory drugs) | | Non-steroidal anti-inflammatory drugs defined by ATC code (EPHMRA) as M01A |
| Alcohol intake | F10, G312, G621, G721, I426, K292, K70, K860, L278, O354, T51, Z714, Z721 | |

Table 7

AF risk score calculation

| Risk score | Disease/condition | Points if present |
|--|---|-------------------|
| CHADS ₂ (9) | Congestive heart failure or left ventricular dysfunction | 1 |
| | Hypertension | 1 |
| | Age \geq 75 years | 1 |
| | Diabetes mellitus | 1 |
| | Stroke (ischemic stroke, transient ischemic disease, or systemic embolism) | 2 |
| CHA ₂ DS ₂ VASc (10) | Congestive heart failure or left ventricular dysfunction | 1 |
| | Hypertension | 1 |
| | Age \geq 65 years | 1 |
| | Age \geq 75 years | 1 |
| | Diabetes mellitus | 1 |
| | Stroke (ischemic stroke, transient ischemic disease, or systemic embolism) | 2 |
| | Vascular disease (myocardial infarction, peripheral arterial disease, or aortic plaque) | 1 |
| | Female | 1 |
| HAS-BLED (10) | Hypertension | 1 |
| | Abnormal renal function | 1 |
| | Abnormal hepatic function | 1 |
| | Stroke (ischemic stroke or transient ischemic attack) | 1 |
| | Bleeding | 1 |
| | Labile international normalized ratio* | 1 |
| | Elderly Age (\geq 65 years) | 1 |
| | Drugs (aspirin, clopidogrel, or non-steroidal anti-inflammatory drugs) | 1 |
| | Alcohol intake | 1 |

*Not included due to unavailable information

Table 8

Definition of concomitant medication

| Drug | Definition | |
|------------------------------------|-----------------------------------|---|
| | ATC code | Generic name |
| Aspirin | - | Aspirin, aspirin dihydroxyaluminum aminoacetate magnesium carbonate |
| Ticlodipine | - | Ticlopidine hydrochloride |
| Cilostazole | - | Cilostazole |
| Clopidogrel | - | Clopidogrel sulfate |
| ARB or ACE | C09A0, C09C0, C09D1 | - |
| Beta blocker | C07A0 | - |
| Amiodarone | - | Amiodarone hydrochloride |
| Procainamide | - | Procainamide hydrochloride |
| Disopyramide | - | Disopyramide, disopyramide phosphate |
| Flecainide | - | Flecainide hydrochloride |
| Pilsicainide | - | Pilsicainide hydrochloride |
| CCB | C08A0 | - |
| Digoxin | - | Digoxin, metildigoxin |
| Diuretics | C03A1, C03A2, C03A3, C03A7, C03A9 | - |
| Statins | C10A1 | - |
| Proton pump inhibitor | A02B2 | - |
| H ₂ receptor antagonist | A02B1 | - |

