| Data sources: MDV clinical database. The database is health insurance claims database. As of end of February 2016, MDV provides commercial | | | |

| | | | |
|---|---|---|---|
| Name of company: Boehringer Ingelheim | | | |
| Name of finished medicinal product: Prazaxa | | | |
| Name of active ingredient: Dabigatran etexilate | | | |
| Protocol date: 6 Jul 2017 | Study number: 1160.0288 | Version/Revision: Version 1.0 | Version/Revision date: Not applicable |
| claims for in and out-patients consisting of medical records from more than 12.94 million patients from 230 large acute care DPC hospitals. . Observation period is planned from 14 March 2010 to 30 June 2016 considering the launch date of dabigatran. | | | |
| Study size: | The previous study 1160.279 was a feasibility study to look into the treatment pattern of OACs in Japan and internal validity of MDV database including availability of co-variates to conduct 1:1 PS matching. For warfarin and dabigatran comparison, the number of AF patients meeting inclusion and exclusion criteria after matching was 4,427 in each cohort. | | |
| Data analysis: | 
This study plans no formal hypothesis testing. The planned analyses are descriptive in nature and results are to be interpreted in an exploratory manner.
 
1:1 Propensity score matching (PSM) was conducted to address potential channelling bias. Outcomes will be assessed in the PSM sample.
 
Patient characteristics prior to and after propensity score matching will be described stratified by treatment group.
 
Patients will be followed up from treatment initiation (index date) to the day of treatment discontinuation (defined as a treatment gap longer than 14 days past the number of days of supply of the last prescription), the day before a switch to a different anticoagulant, the date of disenrollment in MDV, the end of the study period, the occurrence of the event of interest, or death of the patient, whichever occurs first (as-treated analysis).
 
Number of observed events, number of patient years, the corresponding incidence rates and their 95% confidence intervals (CIs) will be reported.
 
Dabigatran and warfarin outcomes will be compared by estimating the hazard ratios (HRs) for the outcomes and their CIs using Cox regression.
 
Kaplan-Meier curves for event-free survival will be estimated.
 | | |

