9.2 SETTING

MDV clinical database is used.

Definition

1. Index date: the date of first oral anticoagulant prescription, namely warfarin or dabigatran
2. Baseline period: 12 months prior to and including the index date
3. Drug exposure period: period of time from index date to the end of drug treatment determined by having continuous record of prescription with less than 14 days of gap in prescription (grace period) or by switching to another OAC (end of index treatment is then considered to occur the day before the prescription of the new OAC)
4. Follow-up period: the day after index date to the earliest of treatment discontinuation, day before switch, end of continuous enrolment in the database, end of study period or death.

Inclusion criteria

1. >18 year-old with confirmed diagnosis of non-valvular atrial fibrillation (NVAF, ICD 10 code I48)
2. New starters of dabigatran or warfarin

Proprietary confidential information © 2017 Boehringer Ingelheim International GmbH or one or more of its affiliated companies

3. No prescription of other OACs for 12 months prior to the index date, defined as the first prescription of OACs (the period is defined as baseline period)
4. Has an index date between 14th of March 2011 to 30 June 2016

Exclusion criteria

1. Having less than 12 months of enrolment prior to the index date
2. Dialysis or kidney transplant recipients in baseline period
3. Having atrial flutter, valvular AF, mechanical valve placement, rheumatic AF, mitral valve prolapse/regurge/stenosis in baseline period
4. Having record of deep vein thrombosis or pulmonary embolism <6 months before AF diagnosis in baseline period

The symptoms, diseases, or treatments in these criteria are defined by ICD-10 code, disease name, or medical care activity name (see Table 1).

Table 1

Definition of symptoms/diseases/treatment for inclusion/exclusion criteria

| Symptoms/diseases/treatment | Definition | | |
|-----------------------------|------------|----------------|--|
| | ICD10 code | Disease name | Medical care activity name |
| Dialysis | - | - | Including “dialysis” |
| Kidney transplant | T861, Z940 | - | - |
| Atrial flutter | - | Atrial flutter | - |
| Valvular AF | - | Valvular AF | - |
| Mechanical valve placement | T820 | - | Including “mechanical valve placement” |
| Rheumatic AF | I05-I09 | - | - |
| Mitral valve prolapse | I340 | - | - |
| Mitral valve regurge | I341 | - | - |
| Mitral valve stenosis | I050, I342 | - | - |

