9.7 DATA ANALYSIS

9.7.1 Main analysis

Propensity Score Matching

[figure not shown]
To reduce channelling bias, dabigatran and warfarin study groups will be established using PS matching method, on a 1:1 fixed ratio. The nearest neighbour method of propensity score matching within a caliper of 0.10 of the standard deviation of the estimated logit will be used to select the matched samples. All pre-defined variables has been evaluated in CTMS 1160.279 for inclusion into the model. Covariates with less than 10 patients present in the data was eliminated as well as CHADs which showed high co-linearity with CHADsVASC which was eliminated from the model. Otherwise, all pre-defined variables will be used. For further detail of the methodology of PS matching, please see the study protocol CTMS 1160.279.

For the primary outcome

Incidence rates of each treatment cohort (warfarin and dabigatran) will be provided, and all analysis will be conducted on the PS matched sample. The hazard ratio (HR) of stroke/systemic embolism for the dabigatran cohort as compared to the warfarin cohort and its 95% confidence interval (CI) will be estimated from the PS matched cohort using a Cox regression model with treatment group as the dependent variable. No additional covariates are considered in the Cox model as no residual imbalance was identified after PS matching (1160.276 study report, c15432368)." There will be no formal hypothesis testing. Kaplan Meier analysis with the number of patients at risk during the follow-up period after the index date and the number of events for ischemic stroke and major bleeding will be provided.

For the secondary outcome

Same analysis method will be utilized to calculate HR for the outcome of major bleeding.

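### The propensity score has no variable for inpatient start or for how recent the last stroke/TIA was, so acute-admission starters can be matched to stable outpatients; size and direction of any bias are unknown

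*Combined protocol and SAP*

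**What the plan says.** Section 9.3.3 lists the covariates of the propensity model. Those that bear on how acutely treatment was started are:

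- "History of hospitalization yes/no". Tables 4 to 8 give no definition for it.
- "History of stroke or transient ischemic attack yes/no". Table 4 defines it by codes only: "Stroke or transient ischemic attack | I60-I64, G45".
- CHA2DS2-VASc and HAS-BLED, which count stroke as present or absent (Table 7).
- "Speciality of prescribers of OAC" and "Time from AF diagnosis to initiation of OAC".

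No look-back is stated for the two history flags. In 9.3.3 only concomitant medication is tied to the baseline period, which 9.2 defines as follows: "Baseline period: 12 months prior to and including the index date".

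The eligibility criteria in 9.2 neither exclude inpatient starts nor require a stroke-free interval. In 9.7.1, sparse covariates and CHADS2 are dropped and nothing is added: "Otherwise, all pre-defined variables will be used". Matching is 1:1 on the score, with no exact matching stated. The Cox model contains treatment only, because earlier work found no imbalance left after matching. The Abstract describes the source as holding "claims for in and out-patients consisting of medical records from more than 12.94 million patients".

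**The concern.** Section 9.1 says that matching deals with channelling bias. Matching can do this only for characteristics in the score, and with an unadjusted Cox model it is the only control. An undated yes/no flag cannot separate a stroke in the current admission from one long past, or an admission still in progress from an unrelated earlier one. The balance table would look complete on these flags even if one arm held more patients started during an acute admission.

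If such patients have a higher early event rate, which is clinically plausible but not documented here, a leftover difference between arms would pass straight into both hazard ratios. Table 9 assumes follow-up of 0.40487 years, about 148 days, so early risk would carry much of the weight.

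The limitations (9.9 and 9.12) concede confounding by factors outside the database. Start setting is different in kind: a source with inpatient and outpatient claims should allow it to be derived.

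**Working it through.** **Step 1: can the mismatch occur?** Compare a patient started on the ward during a stroke admission with an outpatient whose stroke and admission are months old.

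- If the history flags use the 9.2 baseline period (12 months including the index date), both patients score yes on hospitalization and yes on stroke/TIA.
- If the flags leave out the current admission, the ward starter can score no on both and resemble a patient never admitted.

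On either reading, no listed covariate separates current from past. Specialty and time from AF diagnosis may separate some pairs, but neither measures care setting or time since stroke.

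**Step 2: the plan's own reference figures.** Section 9.5 gives a combined hazard ratio of exp(0.21 × ln 0.45 + 0.79 × ln 0.81) = 0.716, which reproduces (0.7159). I read it as dabigatran over warfarin, the direction used in 9.7.1. With Table 9's 4,421 per group, 0.40487 years and 0.03 per year:

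- person-years per arm: 4,421 × 0.40487 = 1,790
- expected warfarin events: 1,790 × 0.03 = 53.7
- expected dabigatran events: 53.7 × 0.716 = 38.4
- total: about 92

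**Step 3: size under assumed inputs.** Let pW and pD be the shares of acute starters left in the matched warfarin and dabigatran arms, and R their event rate relative to other patients, equal in both arms. With constant rates the confounding factor is

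F = [1 + (R − 1) × pW] / [1 + (R − 1) × pD].

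The observed hazard ratio is the true one divided by F. If the two shares are swapped between arms, it is the true one multiplied by F. All shares and rate ratios below are assumptions; the documents give none.

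| Larger share | Smaller share | R | F | 0.716 reads, excess on warfarin | 0.716 reads, excess on dabigatran |
|---|---|---|---|---|---|
| 0.35 | 0.30 | 2 | 1.35/1.30 = 1.038 | 0.690 | 0.743 |
| 0.35 | 0.30 | 3 | 1.70/1.60 = 1.0625 | 0.674 | 0.761 |
| 0.40 | 0.30 | 2 | 1.40/1.30 = 1.077 | 0.665 | 0.771 |
| 0.40 | 0.30 | 3 | 1.80/1.60 = 1.125 | 0.636 | 0.806 |
| equal | equal | any | 1 | 0.716 | 0.716 |

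More extreme inputs give more: 0.40 against 0.20 with R = 5 gives 2.60/1.80 = 1.444, so 0.716 would read 0.496 or 1.034. The documents neither support nor rule out such values. The same F applies to major bleeding with its own R; section 9.5 gives no planning hazard ratio for bleeding.

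**Step 4: size relative to precision.** At the planning values SE(log HR) = √(1/53.7 + 1/38.4) = 0.21. The 5 to 10 point scenarios shift log HR by ln 1.038 = 0.038 to ln 1.125 = 0.118, about 0.2 to 0.6 standard errors.

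**The case against.** The case on the other side has several parts.

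- **Existing control.** Stroke history, any hospitalization, prescriber specialty and time from AF diagnosis are all in the score. A short interval from AF diagnosis would pick up many patients whose AF was first coded in the index admission. This stands: it reduces the imbalance that could remain, and a reader should not infer that start setting and acuity are wholly uncontrolled. It does not supply the missing variables.
- **The window.** A reader might take the flags to be 12-month flags that include the index date. The documents do not say so for these covariates, and that reading is an inference from 9.2. The gap exists with or without it.
- **Bias in favour of dabigatran.** A reader might infer this, because warfarin seems the likelier ward choice. Nothing in the documents shows which drug is started more often in hospital, nor that inpatient starters have more events. The opposite imbalance reverses the bias, and equal shares remove it.
- **Modest size.** In the main scenarios the shift is well inside the sampling error of a study that calls itself exploratory. This stands as to size, but larger samples or pooling would not remove confounding, and wide intervals are no reason to leave out a variable already held.
- **Feasibility.** The outcome rules in 9.3.2.1 link diagnoses to imaging by calendar month, so a 30-day stroke flag may not be derivable as such. This stands and shapes the fix.
- **Unseen material.** Section 9.7.1 refers to the 1160.279 protocol for matching detail, and the contents list shows redacted subsections. A restricted or sensitivity analysis there cannot be excluded. The covariate list itself is intact.

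**Conclusion.** The point holds as a gap in the covariate set that is cheap to close. The propensity model has no variable for inpatient start and none for recency of stroke/TIA. Eligibility does not remove such patients, and the Cox model cannot correct for them. The statement in 9.7.1 that no imbalance remained can speak only to covariates that were measured, so it gives no assurance here.

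The documents do not support a claim that the hazard ratios are in fact biased, or in which direction. Bias needs two things the documents do not report: a difference between the matched arms in ward or post-stroke starts, and a different event rate in those patients. The factor of 1.04 to 1.125 in either direction rests on an assumed 5 to 10 point imbalance, around shares of 30% to 40%, and a rate ratio of 2 to 3. This is a change that should be made, not a defect shown to invalidate the comparison.

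**What to change.** Add two binary covariates to the 9.3.3 propensity model and to the balance table, alongside the existing flags:

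- (a) inpatient on the index date, yes/no;
- (b) stroke/TIA record in the 30 days before the index date, yes/no. If diagnoses are dated only by month, use the index or preceding calendar month and count only records from before follow-up starts. State the rule used where the order within the index month is unclear.

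State the look-back for the existing hospitalization and stroke/TIA flags. Keep the caliper and the 1:1 ratio, rerun the match, and re-check balance on all covariates before relying on the statement in 9.7.1 that none remains unbalanced. If the 1160.279 protocol already handles start setting, a cross-reference in 9.3.3 would do instead.

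Cost: deriving two variables from data that should already be held, and repeating the match and balance check done in earlier work. The matched number may fall somewhat below 4,427; the documents do not allow the loss to be estimated.
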